6.10. Registry Records Retention

The investigator will maintain complete, accurate, and current registry records as required by applicable regulatory requirements. Records will be maintained during the registry and for a minimum of 15 years after the latter of the date on which the registry is terminated or completed, where completion is intended as the last follow-up visit of the last treated subject. In any event, registry records will not be disposed of, nor custody of the records transferred, without prior written sponsor approval.

Investigator records will include, but not be limited to:

- All correspondence with another investigator, an EC, the sponsor, a monitor, or regulatory authority, including required reports.
- Records of each subject's case history and exposure to the device. Case histories include the case report forms and supporting data including, for example, signed and dated consent forms and medical records, including, for example, progress notes of the physician, the individual's hospital chart(s), and the nurses' notes. Such records shall include:
 - Documents evidencing informed consent. In case the consent is waived, a brief description of the circumstances justifying the failure to obtain the informed consent. The case history for each individual shall document that informed consent was obtained or waived prior to participation in the registry.

CONFIDENTIAL INFORMATION

- All relevant observations, including records concerning adverse device effects (anticipated and unanticipated), the information and date and condition of each subject upon entering, and information about relevant previous medical history and the results of all diagnostic tests.
- A record of the exposure of each subject to the device, including the date and time of each use, and any other therapy.
- The protocol, any amendments, and documentation of any deviations from the protocol, including the dates and the reasons for such deviations.
- Any other records that regulatory authority require to be maintained by regulation or by specific requirement for a category of investigations or a particular investigation.
- A signed Investigator Agreement, if applicable
- Any other records as required by the regulatory authority, the EC, and the sponsor.

The investigator will prepare and submit the following reports:

- Protocol deviations shall be reported as described in section 6.7.
- Other: Any other reports as reasonably requested by the sponsor or required by regulatory authority.
- Withdrawal of EC approval: The investigator will report any withdrawal of approval within 5 working days after the investigator has been notified of the withdrawal"

6.11. Publication Plan

The International Committee of Medical Journal Editors (ICMJE) member journals have adopted a trials-registration policy as a condition for publication. This policy requires that all clinical trials be registered in a public trials registry. The sponsor will register the registry and post results as required by applicable regional laws and regulations.

It is the intent of the sponsor that the multicenter results of this registry will be submitted for one or more publications (in a peer reviewed journal). A publications committee will be established to review the multicenter results and develop one or more publications at the completion of the registry. The timing of the multicenter publication may be dependent on regulatory submissions and approvals. Individual sites should coordinate requests for publication through the publications committee or the sponsor/Clinical Science Liaison.

6.12. Health Economics

The sponsor may use registry data to develop a better understanding of the impact that the device may have on clinical practice in order to meet anticipated business needs. With consent of the subject and approval of the supervising EC, billing information may be collected to aid in this evaluation.

7. Data Collection and Submission

The validated Clinical Data Management System (CDMS) for this registry will be provided by [REDACTED] The sponsor keeps a separate Clinical Data Management Plan (CDMP) describing the procedures for verification, validation, and security of the CDMS. The CDMP will describe and document procedures regarding data management processes for this registry.

CONFIDENTIAL INFORMATION

7.1. Data Collection Methods

This registry will report clinical data using the [REDACTED] CDMS web-based application. The CDMS will be the database of record for the protocol and subject to regulatory inspections and quality assurance review. All users will be trained to use the CDMS and will comply with registry specific guidelines / instructions as well as applicable regulatory requirements.

Subject data will be collected using protocol-specific case report forms (CRF). Site staff will enter data directly into the CRF for transmission to the sponsor. The sites will be notified of any significant amendments to the CRFs.

7.2. Data Clarification and Correction

Once entered, data will be evaluated to confirm that it is complete, consistent, and logically sound. If changes to the data in the CDMS are required, all changes, reasons for changes, and persons making the changes will be captured in the CDMS's audit trail. Sponsor will perform periodic data reviews throughout the entire registry. Procedures and documentation for regular and ongoing data review are described in the Clinical Data Management Plan.

7.3. CRF Completion Schedule

All registry data are targeted to be entered into the appropriate eCRF within 10 days of enrollment for the retrospective phase and within 10 days of collection for the prospective phase, however, data outside this window will not be considered a protocol deviation. Pre-Screening information will be recorded for all subjects and will only consist in inclusion /exclusion criteria evaluation, and enrollment information. All subsequent data entry will only occur after collection of informed consent to participate in the registry.

8. Risk Assessment

Given the registry design, subjects would have been already treated at the time of enrollment, therefore there is no potential for physical risks to subjects during the retrospective phase of the registry. T [REDACTED]

There is a minimal risk of [REDACTED] since subject information will be collected and analyzed for the proposed registry. However, appropriate measures will be taken to minimize the risk as much as possible. All information entered into the central registry database will be de-identified. This registry will abide by all regulations related to protecting human subjects and protected health information (PHI).

A complete listing of the known risks associated with the [REDACTED] can be found the IFU.

8.1. Potential Risks

Potential risks were listed in the IFU available at the time of the implant, given the retrospective treatment it is expected that majority of risk are no more applicable because related to the implant procedure. Nevertheless, some device related risks could potentially still occur in the long term i.e (see section Hazards and Adverse Events from IFU):

- Side branch occlusion
- Thrombosis

CONFIDENTIAL INFORMATION

- Infection

8.2. Minimization of Risks

- The sponsor has conducted risk management activities for the [REDACTED] according to ISO14971:2019. Risks remaining after the risk control measures have been implemented are acceptable and the effectiveness of these measures have been verified. The combined impact of the individual risks has been assessed and found to be acceptable. The benefit of the product has been assessed against the overall residual risk and determined that the medical benefit of the product outweighs the risk. The overall residual risk for this product is comparable to similar products. Therefore overall residual risk has been evaluated for the [REDACTED] and has been deemed acceptable. All appropriate methods are in place to collect clinical information during the trial for the [REDACTED]. All risks related to the design, manufacturing and usability of the medical device have been reduced as far as possible.
- The sponsor has performed qualification testing on the device and device components and appropriate quality control measures have been implemented into production. Investigators will be selected who are knowledgeable and experienced in endovascular procedures.
- The site investigator, sub-investigators, study coordinator(s) or designee at each site will be trained to the protocol and subject follow-up requirements.
- Protocol inclusion / exclusion criteria and follow-up schedules are designed to select appropriate subjects and identify potential complications early.
- Safety and efficacy findings during the registry will be shared with the site investigators to aid understanding of the device and potential complications associated with its use.
- Possible interactions with concomitant medical treatments are not expected as such treatment will be consistent with best medical practices and institutional standards. The sponsor will promptly notify the investigator and regulatory authorities of findings that could affect the safety of subjects, impact the conduct of the registry, or alter the IRB / EC's approval to continue the registry.

8.3. Summary of Expected Benefits

Participation in this observational registry is not expected to provide any direct benefits to participating patients. However, the data collected during the registry will foster a better understanding of the performance of the registry device.

8.4. Risk-to-Benefit Rationale

The registry will not require the use of any procedure/follow-up and / or test and / or device different from those required by routine clinical practice for the treated conditions, therefore enrolled patients will not be exposed to additional risks as compared to routine clinical practice.

The clinical data supports an appropriate performance and safety profile and risk-benefit ratio, for the [REDACTED] when used as intended, and the potential benefits offered by the [REDACTED] outweigh the identified potential risks.

CONFIDENTIAL INFORMATION

9. Adverse Events and Safety Monitoring

9.1. Anticipated Adverse Events

Anticipated adverse events are medical complications that are known to be associated with treatment of aortic aneurysms involving the renal-mesenteric arteries using GORE® [REDACTED] as a Bridging Stent with Branched and Fenestrated Endografts. See section 8, Risk Assessment.

9.1.1. Adverse Event Relationship

Each reported AE will be assessed by the investigator for its primary suspected relationship to the device, procedure, disease.

Only one primary relationship will be assigned to each reported AE.

[REDACTED]-related

The functioning or characteristics of the registry device caused or contributed to the adverse event.

Procedure-related

The procedure (and not the device) caused or significantly contributed to the adverse event (e.g., contrast induced renal failure, access vessel complication, etc.)*

[REDACTED] Procedure-related

The procedure (and not the device) to implant [REDACTED] caused or significantly contributed to the adverse event.

Device related ([REDACTED] and Gore accessory)

The functioning or characteristics of the device, other than [REDACTED] and Gore accessory, caused or contributed to the adverse event.

Disease-related

The adverse event was a result of the underlying disease progression for which the registry procedure is being performed, and not the device or procedure.

Gore Accessory related

The functioning or characteristics of the Gore accessory caused or contributed to the adverse event.

Not-related

An adverse event which cannot be attributed to the device, procedure, or disease.

Unknown relationship

The relationship of the adverse event to the device, procedure, or disease insert other categories as appropriate cannot be determined.

*Events related to the specific part of the procedure where [REDACTED] is implanted are not included in this definition

CONFIDENTIAL INFORMATION

9.1.2. Adverse Event Classification

Each AE, regardless of the causal relationship with the device, will be assessed by the Investigator to determine if it is Serious or Non-serious, as defined below. The CEC will review this information and provide a final adjudicated classification.

Clinical Affairs uses the ISO 14155 definition for classification of severity.

Serious Adverse Event

A serious adverse event is an adverse event that led to any of the following:

- (a) death
- (b) serious deterioration in the health of the subject, users, or other persons as defined by one or more of the following:
 - (i) life-threatening illness or injury, or
 - (ii) permanent impairment of a body structure or a body function including chronic diseases, or
 - (iii) in-patient or prolonged hospitalization, or
 - (iv) medical or surgical intervention to prevent life-threatening illness or injury or permanent impairment to a body structure or a body function
- (c) fetal distress, fetal death, or a congenital abnormality, or birth defect including physical or mental impairment

NOTE: Emergency room visits and 23-hour observations may not constitute hospitalization.

Serious Health Threat

Signals from adverse events or device deficiencies are required to be evaluated by the Principal Investigator and reported to Gore immediately

9.1.3. Adverse Event Reporting and Coding

Adverse event reporting begins after enrolment, starting from index procedure date, and ends when the subject completes the 5 years visit. After enrollment all adverse events from the retrospective phase will be reported by the site in the EDC with the initial data entry. Adverse events that occur in the prospective phase will be reported as soon as possible.

For any condition reported in the medical history and / or present at baseline or index procedure do not report as an adverse event unless it becomes serious or increase in intensity, or if a worsening of a baseline condition is reported.

AEs will be reported on the appropriate CRF and documented in the subject's permanent medical record. The investigator at each site is ultimately responsible for reporting AEs to the sponsor.

The following information on each reported AE will be collected:

- Adverse event name
- Adverse event onset date
- Relationship
- Classification serious or non-serious
- Treatment

CONFIDENTIAL INFORMATION

- Outcome
- Resolution date

Adverse events will be coded using the Medical Dictionary for Regulatory Activities (MedDRA).

Adverse event submission guidelines:

- Adverse event reporting begins once the patient is enrolled in the registry. All adverse events should be reported from enrollment through registry completion / discontinuation.
- Provide a diagnosis if possible. If unable to provide a diagnosis, report the symptoms as separate events. Adverse events should be reported using the full name without abbreviations or narratives.
- Adverse events with an outcome status of “ongoing” should be assessed at each follow-up evaluation to determine if the event has resolved. Adverse events ongoing at registry completion / discontinuation should be left as “ongoing” on the AE case report form.

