Number of Subjects	
  
 Subject Cohort	Number patients	Caps per site (patient)	
   
 Fenestrated repair (FEVAR)	100	First cap 10% (10 patients) Second and max Cap 30% (30 patients)	
 
 Branched repair (BEVAR)	120	First cap 10% (12 patients) Second and max Cap 30% (36 patients)	
 
 Fenestrated-branched repair	Up to 40	N.A.	
  
	Subject Cohort	Number patients	Caps per site (patient)	Fenestrated repair (FEVAR)	100	First cap 10% (10 patients) Second and max Cap 30% (30 patients)	Branched repair (BEVAR)	120	First cap 10% (12 patients) Second and max Cap 30% (36 patients)	Fenestrated-branched repair	Up to 40	N.A.
Subject Cohort	Number patients	Caps per site (patient)											
Fenestrated repair (FEVAR)	100	First cap 10% (10 patients) Second and max Cap 30% (30 patients)											
Branched repair (BEVAR)	120	First cap 10% (12 patients) Second and max Cap 30% (36 patients)											
Fenestrated-branched repair	Up to 40	N.A.											
Number of Sites	Up to 15 sites in Europe												
Coordinating PI	
[REDACTED]
 
Contact details and professional position are kept separately from this protocol
												
Registry Duration	
Time to complete enrollment: 8 months, all subjects are enrolled retrospectively
 
Follow-up time: FU data collection up to 5 years. Part of the FU will be prospective.
 
Total registry duration: 5.5 years
												

CONFIDENTIAL INFORMATION

Additional Information	Contract Research Organization (CRO): [REDACTED] [REDACTED] [REDACTED] [REDACTED]
	Electronic Data Capture System: [REDACTED] [REDACTED] [REDACTED]
	Core Lab: [REDACTED] [REDACTED] [REDACTED] [REDACTED]
	Imaging Transfer: [REDACTED] [REDACTED]

CONFIDENTIAL INFORMATION

MD133246 Protocol Template

Revision#: 7

Doc Type: GC

Page iv

LIST OF ABBREVIATIONS

AE	Adverse Event
ADE	Adverse Device Effect
ASA	American Society of Anesthesiologists
BEVAR	Branched endovascular aneurysm repair
CAAA	Complex abdominal aortic aneurysms
CABG	Coronary Artery Bypass Graft
CAD	Coronary Artery Disease
CBC	Complete Blood Count
CDMS	Clinical Data Management System
CE	Conformité Européenne
CEC	Clinical Events Committee
CFR	Code of Federal Regulations
CIP	Clinical Investigation Plan
cm	Centimeters
CRF	Case Report Form
CRO	Contract Research Organization
CT	Computed Tomography

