CTA	Computed Tomographic Angiography
DTA	Descending Thoracic Aortic
EC	Ethics Committee
EDC	Electronic Data Capture
eCRF	Electronic Case Report Form
ePTFE	Expanded Polytetrafluoroethylene
ESVS	European Society for Vascular Surgery
EU	European Union
FEVAR	Fenestrated endovascular aneurysm repair
FDA	Food and Drug Administration (United States)
Fr	French (sizing)
GCP	Good Clinical Practice
GIS	Gore Imaging Sciences
HE	Health Economics
ICF	Informed Consent Form
ICH	International Conference on Harmonization

CONFIDENTIAL INFORMATION

IFU	Instructions for Use
LAR	Legal Authorized Representative
LSA	Left Subclavian Artery
MDD	Medical Devices Directive
MDR	Medical Devices Regulation
MI	Myocardial Infarction
mm	Millimeters
MRI	Magnetic Resonance Imaging
OMA	Office of Medical Affairs (W. L. Gore & Associates, Inc.)
PG	Performance Goal
PHI	Protected Health Information
PI	Principal Investigator
SAE	Serious Adverse Event
SVS	Society of Vascular Surgery
TAAA	Thoraco-Abdominal Aortic Aneurysms
TIA	Transient Ischemic Attack
USADE	Unanticipated Serious Adverse Device Effect

CONFIDENTIAL INFORMATION

DEFINITIONS

Adverse Event: Untoward medical occurrence, unintended disease or injury, or untoward clinical signs (including an abnormal laboratory finding) in subjects, users, or other persons, whether or not related to the investigational medical device whether anticipated or unanticipated. This definition includes events related to the investigational medical device and events related to the procedures involved

Adverse Device Effect: Adverse event related to the use of an investigational medical device

Clinical Investigation Plan: A set of documents that describes the rationale, objectives, design and proposed analysis, methodology, monitoring, and the plan for the conduct of a clinical investigation. These documents may include the protocol, monitoring plans, and statistical analysis plans.

Device Deficiency: Any inadequacy in the identity, quality, durability, reliability, safety, or performance of an investigational device, including malfunction, use errors, or inadequacy in information supplied by the manufacturer.

Enrollment: A patient is considered enrolled into the registry once informed consent has been signed and dated or consent is waived.

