3.4.3. Secondary Endpoints

Secondary performance outcomes

- Reintervention (total and reintervention that can be attributed to branches originally treated with the [REDACTED]) at 12 months and annually through 5 years post-implant
- Target Vessel Technical Success
- Primary Technical Success (Total Endovascular Procedure)
- Target vessel instability at 12 months and annually through 5 years post-implant
- Target vessel patency, patient level, annually from 2-5 years post-implant (extended primary endpoint)
- Target vessel patency, vessel level analysis, annually from procedure to 5 years post-implant

Secondary safety outcomes

- Aneurysm-related mortality at 12 months and annually through 5 years post-implant
- MAEs at 30 days

CONFIDENTIAL INFORMATION

4. Registry Population

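### Protocol Section 9.1.3 states two conflicting adverse-event windows; a site that takes the submission guideline literally would omit events between treatment and consent

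*Protocol*

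**What the plan says.** Protocol Section 9.1.3 addresses the adverse-event period in two places.

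- **Opening paragraph.** "Adverse event reporting begins after enrolment, starting from index procedure date, and ends when the subject completes the 5 years visit". The next sentence adds: "After enrollment all adverse events from the retrospective phase will be reported by the site in the EDC with the initial data entry".
- **Submission guidelines, first bullet.** "Adverse event reporting begins once the patient is enrolled in the registry". It continues: "All adverse events should be reported from enrollment through registry completion / discontinuation". The bullet does not mention the index procedure.

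The Definitions fix what enrolment means: "A patient is considered enrolled into the registry once informed consent has been signed and dated or consent is waived". The protocol summary gives the order of events: "Time to complete enrollment: 8 months, all subjects are enrolled retrospectively". The opening of Section 8 confirms it: "Given the registry design, subjects would have been already treated at the time of enrollment".

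The safety endpoint concerned is "MAEs at 30 days", a secondary safety outcome in Protocol Section 3.4.3 and SAP Section 2.3.

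**The concern.** In a prospective study, a rule to report events from enrolment onward is routine, because treatment follows enrolment. Here the order is reversed, and the same words remove the perioperative period. That is where the 30-day MAE endpoint lies.

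The bullet belongs to the list labelled as submission guidance, so site staff may well treat it as their working instruction. If some sites follow the opening and others the bullet, non-fatal 30-day event rates will differ by site for reasons unrelated to the device. The pooled rate will then err in the favourable direction.

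The analysis would not correct this. SAP Section 4.0 analyses the available data, and an event that was never entered counts as no event rather than as a missing value. The Clinical Events Committee (Protocol Section 9.4) checks the consistency of endpoints that sites report, so an unreported event may never reach it.

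**Working it through.** The plan gives no figure to reproduce, so the check sets the two windows side by side.

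**1. Start and end of each window**

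| | Opening of 9.1.3 | Submission bullet, read literally |
|---|---|---|
| First event counted | index procedure | consent or waiver |
| Last event counted | 5-year visit | completion or discontinuation |

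The end points agree for completers, because Section 5.14 defines completion by the 5-year visit. The conflict is in the start.

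**2. What lies between the two starts.** Section 5.9 defines the retrospective phase as running from treatment to the consent signature. The literal bullet omits exactly that phase.

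**3. Where the 30-day window falls.** Let g be the number of days from implant to consent.

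- If g > 30, the whole 30-day window precedes enrolment and is omitted.
- If g ≤ 30, only the first g days are omitted.

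The public text gives no enrolment start date, so g > 30 is an assumption. All patients were treated before enrolment and the inclusion period goes back to January 2017, so it should hold for most or all of them.

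**4. Patients dead at registry entry.** They enter by next-of-kin consent or waiver (Sections 3.3 and 4.2). All their events precede enrolment, so the literal bullet captures none of them. This step needs no assumption about g.

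**5. Which MAE components are exposed.** Section 3.4.1 lists all-cause mortality, myocardial infarction, respiratory failure, renal deterioration, bowel ischaemia, paraplegia and stroke. Under Section 9.1.4 death is not itself an adverse event, so mortality depends less on this rule. The other components are the exposed ones.

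**6. Form of the bias.** Let p be the true non-fatal 30-day MAE rate, and f the share of patients at sites that apply the bullet literally. If g > 30 for everyone and p is the same across sites, then

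observed rate = p × (1 − f), and understatement = p × f.

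At f = 0 the observed rate is p; at f = 1 it is 0. The documents give neither p nor f, so no narrower range can be supported.

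**7. Primary endpoint.** Twelve-month patency is tested on imaging and loss of patency (Protocol Section 10.1; SAP Section 5.0). It does not depend on this rule.

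**The case against.** The strongest reply is that Section 9.1.3 already answers the question. Its second sentence expressly orders entry of retrospective-phase events. Section 5.9 has treatment and follow-up data collected back to the time of treatment, Section 5.11 collects all follow-up between procedure and consent from the chart, and Section 7.3 sets a 10-day entry target for retrospective data. On that view, the bullet only says when sites submit reports: its first sentence echoes the opening, where enrolment clearly refers to the act of reporting. The literal reading would also leave no reportable event in deceased patients, whom Section 3.3 deliberately brings in.

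Much of this stands. The intent is clear, and a reader who infers that the protocol as a whole drops 30-day MAEs goes further than the text allows. It does not make the bullet harmless. If both its sentences concern timing, the second largely repeats the first. The second is worded as a rule about which events to report, and nothing in it points back to the index procedure.

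Three other inferences should also be resisted.

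- **Thirty-day aneurysm-related mortality is not a separate endpoint.** Section 3.4.3 assesses aneurysm-related mortality at 12 months and annually to 5 years. Thirty days appears only within its definition.
- **Reintervention data do not hang on this bullet.** Section 5.10 separately requires reinterventions, and the adverse events leading to them, to be documented.
- **The gap would not necessarily be invisible.** Onset dates are collected, and Section 6.4 provides central review for completeness and outliers. A site with no event before consent could stand out. The safeguard is partial, since only specific critical variables are source verified.

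**Conclusion.** Section 9.1.3 is internally inconsistent and should be corrected. Read literally, the bullet excludes events from treatment to consent: all events in patients dead at entry and, assuming consent more than 30 days after implant, all non-fatal 30-day MAEs in the others. Because the remaining text points the other way, the realistic consequence is inconsistent reporting between sites that understates non-fatal 30-day MAEs, not their wholesale loss. The amount depends on how many patients are at sites that follow the bullet, which cannot be estimated from the documents. Mortality is less exposed, and the primary hypothesis test is untouched. This is a wording conflict, not a flaw in the chosen design.

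**What to change.** Replace the first submission-guideline bullet with a sentence that separates when data are entered from when events occurred, for example: *After enrolment, report all adverse events with onset from the index procedure date through registry completion or discontinuation, including those before consent.* Remove the statement that reporting begins at enrolment wherever it could be taken to define the event period. Use the same sentence in the CRF guidelines.

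The cost is one protocol sentence, with ethics committee approval of the amendment under Section 6.8, and a reminder to sites. No new data source is needed, because the chart review already covers this period. For data already entered, a count by site of adverse events with onset before consent would show whether any site has followed the bullet literally.
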